#### 3.1 Study design

This study is a multi-center, randomized, double-blind, parallel group, active comparator trial designed to evaluate the overall effect of LCZ696 compared to valsartan on cognitive function as assessed by a comprehensive cognitive battery in patients with HFpEF (Figure 3-1). The study population will consist of patients  $\geq 60$  years of age with chronic symptomatic HF (NYHA class II-IV) and a left ventricular ejection fraction (LVEF)  $>40\%$ . Patients will be randomized in a 1:1 fashion to either LCZ696 200 mg bid or valsartan 160 mg bid.

Cognitive function will be assessed at baseline and every six months up to 3 years by a comprehensive cognitive battery, and MMSE will be assessed annually. Patients scoring  $<24$  on the MMSE scale during screening will be excluded from the study. Patients will be stratified based on age ( $< 75, \geq 75$  years), MMSE score ( $< 28, \geq 28$ ), and if participating in the PET imaging substudy, amyloid status (amyloid positive/negative). APOE4 is a strong predictor of cognitive impairment (Lim et al 2015) and A $\beta$  accumulation. Therefore, patients will be genotyped for APOE4 allele status.

[figure not shown]
The study will also evaluate the impact of LCZ696 therapy compared to valsartan on  $\beta$ -amyloid deposition in the brain using florbetapir  $^{18}\text{F}$  PET imaging in a subset of patients. PET imaging requires specialist centers experienced in the technique that are in close proximity to a radiopharmaceutical production facility, thus a subset of centers will be selected as PET centers. To ensure high quality of imaging data, PET imaging will be conducted in all eligible patients at selected PET capable centers. Amyloid PET imaging will be performed at randomization, at 18 months, and at 3 years (EOS Visit). If a patient permanently discontinues treatment prior to 3 years, a PET scan should be done at the end of treatment visit (EOT visit) if a prior scan was performed more than twelve months ago. End of study (EOS) scan will not be required if EOT scan is performed within 12 months of end of study visit. All PET scans will be evaluated centrally.

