### **6 Visit schedule and assessments**

Table 6-1 lists all of the assessments and indicates with an "x" when the visits are performed.

Patients/subjects must be seen for all visits on the designated day, or as close to it as possible. Missed or rescheduled visits should not lead to automatic discontinuation.

[figure not shown]
After randomization, study drug discontinuation (permanent or temporary) for any reason does not constitute withdrawal from the study and should not lead to the patient being withdrawn from the study. Patients who discontinue study drug should be requested to return for an End of Treatment visit (EOT) in which all of the assessments outlined in Table 6-1 will be performed.

Patients who prematurely discontinue the study for any reason should be scheduled for a visit as soon as possible, at which time all of the assessments listed for the end of study visit will be performed. At the end of study visit, all dispensed investigational product should be reconciled and the adverse event and concomitant medications reconciled on the CRF.

Every effort should be made to complete end of treatment (EOT) assessments within 3 months of the last study drug dose for patients who have discontinued study drug permanently. Patients who terminate study drug early are expected, and should be encouraged to, attend all the remaining protocol specified study visits and perform all measurements as stipulated in the visit schedule (Table 6-1).

For EOT / End of Study (EOS) visit, the PET and MRI scans will only be performed if prior scans were performed more than twelve months ago. The CCB, [REDACTED] FAQ, [REDACTED] assessments will only be performed if prior assessments were performed more than three months ago.

Documentation of attempts to contact the patient should be recorded in the source documentation.

After identifying a potential patient, an informed consent form (ICF) must be signed by the patient before performing all study-related screening. The AE and serious adverse event (SAE) reporting period begins at the time the ICF is signed.

A Visit 199 (end of run-in visit) will be completed for all patients who enter the treatment run-in epoch. For patients who discontinue during the treatment run-in epoch or who are not able to be randomized due to safety reasons, Visit 199 will be their discontinuation visit.

For patients that will be randomized, Visit 199 will be their end of treatment run-in disposition visit.

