As sensitivity analysis, the change in a cortical composite SUVR from baseline to 3 years will also be analyzed based on a repeated measures ANCOVA model in which treatment, age stratification factor, MMSE stratification factor, region, baseline cerebrovascular disease burden as measured by MRI, APOE4 status (carrier vs. non-carrier), baseline amyloid status (positive/negative), visit (18 months, 3 years), and treatment-by-visit interaction will be included as fixed-effect factors and baseline value and baseline-by treatment as covariates, with a common unstructured covariance matrix among visits between treatment group. The adjusted mean changes at 3 years (Week 156) within each treatment, the difference in mean changes at 3 years (Week 156) between two treatments, its 95% confidence interval obtained from the above model will be presented. The analysis is based on likelihood method with an assumption of missing at random for missing data. A three month window will be applied to re-map any unscheduled visit assessments to a missing scheduled visit assessment.

In addition, to assess the sensitivity of the MAR assumption used in multiple imputation, analyses based on multiple imputations, such as those using a pattern mixture model approach,

may be performed, which assumes that missing values after death, HF hospitalizations, stroke were missing not at random (MNAR).

A shift table to summarize the proportion of patients' amyloid status change over time from baseline by treatment will be provided as well.

All analyses will be performed in patients in the Safety set who participate in the PET image substudy, including 'on-treatment' data only. On-treatment data refer to the SUVR values obtained while patients are on-study-medication (regardless of treatment interruption) or within six months after final study drug intake date.

[figure not shown]

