In all the analyses planned in this document, on-treatment data refer to data collected while patients are on-study-medication (regardless of treatment interruption) or within a specified window after final study drug intake date based on the endpoint of interest.

- For cortical SUVr [REDACTED] based endpoints, data collected within 6 months after final study drug intake date will be considered as on-treatment data.
- For all other primary, secondary and exploratory endpoints, data collected within 3 months after final study drug intake date will be considered as on-treatment data.

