2.7.1 Change from baseline in SUV_r at 3 years

PET amyloid brain scans will be performed at randomization visit, at 18 months, and at end of study visit (scheduled at 3 years) for the patients participating the PET imaging sub-study and with non-missing baseline. In addition, for patients who have premature permanent discontinuation of study drug, it is planned to obtain an end-of-treatment PET scan if the next scheduled PET scan is < 6 months after treatment discontinuation. In order to make the most use of data collected from all available PET scan assessments, including the planned 'end-of-treatment' and 'end-of-study' assessments, the analysis of change from baseline (randomization) in a cortical composite SUV_r at 3 years (Week 156) will be based on a model-based multiple imputation approach under the MAR (missing at random) assumption. Further sensitivity analyses will be provided to assess the robustness of the MAR assumption on the missingness

mechanism. Following table provides an overview of missing data handling for cortical composite SUVr data with corresponding assumptions on missingness.

Table 2-4 Overview of missing data handling in analysis of change from baseline in SUVr at 3 years

Analysis	Analysis Set	Data excluded	Missingness assumption	Analysis method	Time points included	Imputed dataset required?
Estimand: The treatment effect had all patients stayed 'on-treatment' for the 3-year planned follow-up duration (Under 'as-treated' principle)						
Primary	SAF (restricted to PET imaging substudy)	Off-treatment (>6 months after last dose)	MAR	MI followed by ANCOVA	Baseline, Month 18, Year 3, and all other post-BL measurements <= 6 months after last dose	Yes
Sensitivity	SAF (restricted to PET imaging substudy)	Off-treatment (>6 months after last dose) Data outside 6-months window from scheduled visit	MAR	Repeated measure ANCOVA	Month 18, Year 3	No
Sensitivity	SAF (restricted to PET imaging substudy)	Off-treatment (>6 months after last dose)	MNAR for missing due to death, HF hospitalization and stroke - tipping point analysis	MI (tipping point analysis) followed by ANCOVA	Baseline, Month 18, Year 3, and all other post-BL measurements <= 6 months after last dose	Yes
Estimand: Measurement of treatment effect of interest MAR = Missing At Random; MNAR = Missing Not At Random; MI = Multiple Imputation						

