In addition, to assess the sensitivity of the analysis results to the MAR assumption used in the multiple imputation for primary analysis method, a tipping point analysis will be performed on the change from baseline in SUVr which assumes that missing values after death, HF hospitalization and stroke are missing not at random (MNAR). This analysis will follow the same procedure as described in [section 2.5.5](#) for the primary endpoint, with the exception that the imputations under MAR are obtained from a regression based imputation as described in the primary analysis method of this endpoint ([Section 2.7.1](#)). The analysis will be repeated for varying penalty factors in a range between 1 and 1.6.

[figure not shown]
If convergence issue arises in any of above described supportive analyses, the handling approach described in [Section 2.7.1](#) will be used to address the convergence issue.

[figure not shown]
Furthermore, to assess the sensitivity of the analysis results to the randomization stratification that is done incorrectly due to transcription error or inconsistent site and central reviewer readings, analysis described in [Section 2.7.1](#) will be repeated using the final data entered in the clinical database, instead of the stratification factors based on IVR system.

[figure not shown]
To address missing assessments due to COVID-19 pandemic, the analysis mentioned in [Section 2.7.1](#) will be repeated using PET substudy set with a wider assessment window extending from 6 months to 9 months for assessments that are scheduled to take place starting Mar 1, 2020 and onwards. This also applies to the data excluded from analysis if assessment is done more than 9 months after last study drug intake instead of 6 months.

[figure not shown]
All analyses will be performed in patients in the Safety set who participate in the PET image substudy and with non-missing baseline, including ‘on-treatment’ data only. On-treatment data refer to the SUVr values obtained while patients are on-study-medication (regardless of treatment interruption), or within defined window in each supportive analysis (six months or nine months) after the final study drug intake date.

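### No SUVr model uses scans taken more than 6 months (9 in one COVID-19 variant) after the last dose, and none is as-randomised with all data

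*SAP*

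**What the plan says.** - **Data rule.** SAP 2.7.1.1: "All analyses will be performed in patients in the Safety set who participate in the PET image substudy" and have a non-missing baseline, restricted to on-treatment data. Protocol 9.5.2 has the same restriction: "All analyses will be performed in patients in the Safety set who participate in the PET image substudy, including" on-treatment data only. The Safety set groups patients by the drug they actually received (SAP 2.2).
- **Window.** SAP 2.1.1, for cortical SUVr: "data collected within 6 months after final study drug intake date will be considered as on-treatment data". One COVID-19 supportive analysis in SAP 2.7.1.1 widens this for assessments scheduled from 1 March 2020: "This also applies to the data excluded from analysis if assessment is done more than 9 months after last study drug intake".
- **Estimand.** SAP Table 2-4 names one, the effect if everyone had remained on drug for three years. All three of its rows exclude scans more than six months after the last dose.
- **Which scans exist.** Scans are scheduled at months 0, 18 and 36. After permanent discontinuation, Protocol 3.1 calls for an EOT scan "if a prior scan was performed more than twelve months ago", and waives the end-of-study scan if the EOT scan lies within 12 months of it. Protocol 6.5.1 applies the 12-month spacing to month 18 as well. Patients who stop drug early are expected to "attend all the remaining protocol specified study visits and perform all measurements" (Protocol 6). SAP 2.7.1 gives a different EOT trigger: the next scheduled scan is less than six months after discontinuation.
- **Other endpoints.** GCCS has a second, intention-to-treat estimand with a FAS all-data model (SAP Table 2-3 and 2.5.4). The domains and FAQ have one too (SAP 2.6.2). Plasma amyloid keeps all data (SAP 2.11).
- **Figures.** Protocol 9.5.1 lists SUVr among the endpoints to be plotted in both SAF (on-treatment) and FAS (all data). SAP 2.6.2 has the matching list without SUVr, and SAP section 4 records no change to protocol analyses.

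**The concern.** Protocol 3.2 and 6.5.1 call SUVr a key secondary endpoint, and the protocol treats amyloid accumulation as a process measured over years. A 3-year scan taken after stopping drug therefore still carries information on the effect of assignment. When that scan is set aside, the 3-year value is imputed under missing at random from the on-treatment model.

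The SUVr tipping-point analysis stresses that assumption only for death, heart failure hospitalisation and stroke (SAP 2.7.1.1). No SUVr analysis tests it for drug discontinuation, although observed scans that could do so will have been collected. For GCCS, the domains and FAQ, the FAS all-data model does this job. Discontinuation is not a remote possibility: Protocol 3.2 cites earlier heart failure data with more than a third of patients off study drug by three years.

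**Working it through.** **1. The plan's own figure.** Inputs from SAP 3.2 and 3.3: margin 0.01, SD 0.03, true difference 0, two-sided 95% CI, 300 complete patients (150 per arm), 30% loss, 430 randomised.
- SE = 0.03 × √(2/150) = 0.00346. Probability = Φ(0.01/0.00346 − 1.96) = Φ(0.93) = 82.3%, so the stated minimum of 80% holds.
- 300/0.70 = 429, against 430 stated; 430 × 0.70 = 301.

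**2. Fate of scans by month of stopping, t.** Protocol scan rules, six-month window, EOT visit on the stopping day:

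| t | EOT scan | Month-18 scan | Month-36 scan | Usable after baseline |
|---|---|---|---|---|
| under 12 | none (baseline scan not over 12 months old) | taken, excluded (18 − t > 6) | taken, excluded | none |
| 12–18 | taken, used | not due (EOT scan under 12 months earlier) | taken, excluded (36 − t ≥ 18) | EOT |
| 18–30 | none (month-18 scan not over 12 months old) | used | taken, excluded (36 − t > 6) | month 18 |
| 30–36 | taken, used | used | not required | month 18 and EOT |

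Assume t is uniform over 36 months. The month-36 scan is excluded for 30/36 = 83% of discontinuers who keep attending, and 12/36 = 33% have no usable post-baseline scan.

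**3. Later EOT visit.** EOT assessments may fall up to three months after the last dose (Protocol 5.6.2 and 6). At three months, patients stopping from month 9 or from month 27 already meet the 12-month rule and get a usable EOT scan. The shares become 27/36 = 75% and 9/36 = 25%. The nine-month window also gives 27/36 = 75% for the month-36 scan.

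**4. Number of scans.** The 30% loss pools death, loss to follow-up, drug discontinuation and start of AD treatment (SAP 3.3), and the split is not given. 430 × 0.30 = 129. Assume 25% to 100% of these stop drug and keep attending, that is 32 to 129 patients.
- Month-36 scans excluded: from 32.25 × 27/36 = 24 to 129 × 30/36 = 108, or 6% to 25% of 430.
- Patients with no usable post-baseline scan: from 32.25 × 9/36 = 8 to 129 × 12/36 = 43.

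**5. Precision, for scale only.** Half-width = 1.96 × 0.03 × √(4/N), counting observed 3-year values. N = 301 gives 0.0068; N = 301 + 24 = 325 gives 0.0065; N = 301 + 108 = 409 gives 0.0058. Adding off-drug scans changes the estimand, so this is not simply a gain in power.

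**6. The two EOT triggers.** With scans 18 months apart, a prior scan over 12 months old and a next scan under 6 months away are the same condition (18 − 12 = 6) if the EOT visit is on the stopping day. They diverge when the visit is later. A patient who stops at month 10 and attends at month 13 gets a scan under Protocol 3.1 (13 months since baseline) but not under SAP 2.7.1 (month 18 is 8 months after stopping).

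**The case against.** The best defence is that the restriction is deliberate. Both documents analyse SUVr as a safety endpoint, state an on-treatment rule consistently in the SUVr sections, and aim to exclude an excess of 0.01. If the drug raised amyloid, time off drug would tend to dilute the difference and make exclusion easier. That stands, and it is why on-treatment should remain primary.

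Two further points stand in part. FAS is not simply the larger set, because SAP Tables 5-1 and 5-2 remove patients at sites closed for GCP reasons from FAS but not from SAF. As-treated and as-randomised grouping differ only for patients given the other arm's drug. The substance is therefore the excluded scans more than the grouping.

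Stronger readings are tempting, but the documents do not support them:
- A reader might infer that scans after discontinuation are never analysed. Scans within six months (nine in one variant) count as on-treatment. That covers EOT scans done within three months, and SAP 2.7.1.1 also summarises EOT values separately.
- A reader might infer that discontinuers are imputed only from patients who tolerate the drug. The imputation model in SAP 2.7.1 is fitted within arm, with a random intercept and slope on actual scan time. A discontinuer with a usable scan is imputed partly from their own trajectory.
- A reader might infer that unequal stopping between arms would go unseen. SAP 2.4.1 plans Kaplan-Meier estimates of permanent discontinuation by arm, and SAP 2.3.1 plans PET-substudy disposition by arm. These show whether stopping differs, but not whether it moves the SUVr comparison.

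**Conclusion.** The gap is real but limited. Every SUVr model is on-treatment and as-treated, scans beyond the window enter none of them, and no as-randomised all-data SUVr estimate is planned, unlike for GCCS, the domains and FAQ. This does not invalidate the primary SUVr analysis. It leaves one missing-data assumption, for drug discontinuation, untested when scans exist to test it.

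That finding rests on the text alone. Its size rests on two assumptions that the documents do not settle: uniform timing of discontinuation, and the share of the 30% loss that is discontinuation with continued attendance. The top of the range, 108 scans, takes the whole 30% as such patients and is an upper bound, since those who die or are lost provide no 3-year scan. A supportive analysis is a cheap improvement worth making.

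**What to change.** Keep the on-treatment analysis as primary. Add to SAP Table 2-4 and 2.7.1.1 one supportive SUVr analysis in FAS patients of the PET substudy with non-missing baseline, by randomised arm, using all scans at their actual times whatever the interval since last dose. Label it a treatment-policy estimand. State how the imputation model treats time after stopping, because the present single slope per patient has no term for it, and note the handling of sites closed for GCP reasons.

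Reconcile Protocol 9.5.1 (SUVr figures in FAS with all data) with Protocol 9.5.2 and SAP 2.6.2, 2.7.1.1 and section 4. Reconcile the EOT-scan triggers in Protocol 3.1 and SAP 2.7.1, since they decide which scans exist.

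The cost is a short specification, a FAS-based PET flag and one more run on scans already collected. SAP version 5.0 is dated before database lock. The downside is a second estimate that off-drug time may dilute, so it should be read beside the on-treatment result and not replace it.

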2.7.3 Deaths

Patients that died during the study period will be reported separately for run-in and double-blind treatment epochs. Deaths occurring during the double-blind treatment epoch will be summarized by actually received treatment group to present number and percentage of patients that died by overall and reason categories (CV/non-CV causes as reported by investigator). In addition, listings will be provided for patients that died during the study period with the primary reason of death.

The analysis will consider all patients in the Safety set (SAF) for reported deaths during the double-blind treatment epoch while deaths during the run-in epoch will be reported based on patients in the Enrolled set (ENR).

2.8 Pharmacokinetic endpoints

Not applicable

[figure not shown]
2.9 PD and PK/PD analyses

Not applicable.

2.10 Patient-reported outcomes

Following Patient reported outcomes (PRO) are collected by sites at respective visits.

1. Instrumental activities in daily life (IADL) as assessed through Functional activity questionnaire (FAQ)

[figure not shown]
Analysis method for outcome (1) has been outlined in [section 2.6.2](#) for secondary endpoints. The analysis methods for other outcomes will be described in [Section 2.12](#) as part of the exploratory endpoint analyses.

[figure not shown]
2.11 Biomarkers

[figure not shown]
For plasma A β 1-40, the log-transformed ratio to baseline i.e. $\log(\text{post-dose value}/\text{baseline})$ will represent the change from baseline in logarithmic change for each subject at every post-dose time point. The change from baseline to a pre-defined time-point (Weeks 13, 52, 104 and 156) in logarithmic scale will be analyzed using a repeated measures ANCOVA model in which treatment, age stratification factor, MMSE stratification factor, education level, APOE4 status (carrier vs. non-carrier), visit (Weeks 13, 52, 104 and Week 156) and treatment-by-visit interaction are included as fixed-effect factors and baseline log-transformed plasma A β 1-40 and visit by baseline log-transformed plasma A β 1-40 interaction as covariates, with a common unstructured covariance matrix among visits between treatment groups. The adjusted mean changes within each treatment, the difference in mean changes between the two treatments, and its 95% confidence interval obtained from the above model will be presented for all the assessment visits. All the estimates will be back-transformed to natural scale for reporting.

[figure not shown]
Descriptive summaries of absolute values and change from baseline in A β 1-40 by treatment group and visit will be presented using summary statistics (n, mean, SD, median, minimum, maximum, Q1, Q3, geometric mean and Coefficient of Variation). Mean A β 1-40 levels will also be graphically presented by each visit over study period for each treatment group.

[figure not shown]
All of the above analyses will be performed for patients for whom the biomarker data is obtained in the PET imaging substudy with non-missing baseline including all data.

